## 4.2 Scientific Rationale for Study Design

Since the dosage and administration of this FDC is expected to be a second-line therapy in China, MK-0653C will be administered when participants are not well controlled with monotherapy of atorvastatin. The target population of this trial is participants with hypercholesterolemia in whom the lipid management target value of LDL-C as per their CAD-risk category based on Chinese Guidelines on Prevention and Treatment of Dyslipidemia in Adults has not been achieved, judging from the results of laboratory tests after atorvastatin run-in period and the presence/absence of CAD history.

### 4.2.1 Rationale for Endpoints

#### 4.2.1.1 Efficacy Endpoints

The primary objective of this trial is to demonstrate superiority of lipid-modifying efficacy of MK-0653C 10/10 mg or 10/20 mg as compared to of atorvastatin monotherapy at twice the atorvastatin dose contained in MK-0653C monotherapy in hypercholesterolemia participants who are not well controlled by the atorvastatin monotherapy. In this trial, the percent change in LDL-C at week 12 from baseline will be used as the primary efficacy endpoint considering the maximum efficacy will be reached at that time point; the percentage of participants achieving their LDL-C goals will be used as the exploratory efficacy endpoint.

LDL-C lowering therapy especially with statin has been proved to be effective for the primary and secondary prevention of Coronary Artery Disease [Stamler, J., et al 1986] [Kannel, W. B., et al 1979] [Castelli, W. P., et al 1983] [Okamura, T., et al 2007]. LDL-C is positioned as a valid biomarker for lipid management, and is used as an important variable for the development of lipid-improving drugs in China, as well as in other countries outside China. In statin studies, the relationship between LDL-C level and the prevention of arteriosclerotic diseases has been well established. The efficacy evaluation based on the percent change in LDL-C as the primary variable has been commonly used in the previous clinical studies of ezetimibe and statins.

#### 4.2.1.2 Safety Endpoints

The safety will be evaluated with clinical and laboratory safety assessments conducted throughout the trial. Centralized liver function test and other biochemistry test will be done at Visit 3, Visit 5 and Visit 6 to detect potential hepatic adverse events and muscle adverse events which were defined as AE of interest. The rational of arrangement is based on the facts as follow. Atorvastatin and Ezetimibe, as the active ingredients, have been authorized and widely used in China as well as worldwide for many years with well-established safety profile. A consistent safety profile is expected of this FDC. According to the label of atorvastatin, the majority of liver function abnormality occurs in first 3 months post the 1st dose, liver function test is suggested to be performed prior to initiation and at 3 month as a standard recommendation according to the label. Atorvastatin, like other statins, occasionally provoke myopathy and rhabdomyolysis, especially concomitant use with cyclosporine or potent CYP3A4 inhibitors like clarithromycin. However, surveillance of creatine kinase (CK) cannot prevent the occurrence of myopathy or rhabdomyolysis. Regular surveillance of CK is only recommended when those drugs mentioned above are prescribed for concomitant use as recommended in the label. Ezetimibe was generally well tolerated and when given as concomitant use with statin physicians should refer to the directions for use of statin according to the ezetimibe label. In addition, unnecessary blood test cause participant's burden and can potentially cause the procedure related adverse event, e.g. injection site reaction and negative impact on the willingness of participation.

In addition to the centralized lab test according to the scheduled visits, qualifying local lab can be used to evaluate the eligibility during the screening and also to detect the safety signal during the trial conduction when needed.

Clinical measurements include monitoring of vital signs/physical examination at each visit will be done. Tiered methods will be used for safety endpoints analysis according to severity, frequency and relationship with the drug.

#### 4.2.2 Rationale for the Use of Comparator/Placebo

The Comparator used in this trial is atorvastatin (Lipitor®). Atorvastatin is one of the active components of MK-0653C. In order to demonstrate the additional contribution of the 2nd active component (ezetimibe) in an FDC (MK-0653C), it is commonly required by the agency to demonstrate the superior lipid-modifying efficacy of the FDC compared to

continuing atorvastatin monotherapy (same dose or double dose) in hypercholesterolemia participants who are not well controlled by prior atorvastatin monotherapy. In this trial, atorvastatin 20 mg and 40 mg are being used as the comparators to MK-0653C 10/10 mg and 10/20 mg separately. Please refer to the approved label of Lipitor® for more information about the dose and usage of atorvastatin.

#### **4.3 Justification for Dose**

In this trial, MK-0653C 10 (ezetimibe)/10 mg (atorvastatin) and 10 (ezetimibe)/ 20 mg (atorvastatin) were selected. The dosage of ezetimibe is 10 mg once daily. Ezetimibe (EZETROL®) at dose of 10 mg has been approved in China since 2006; it is the only approved dose in China and has an abundance of clinical use experience both as monotherapy and combination therapy in Asian patients.

The brand atorvastatin product, Lipitor® tablets, has been marketed since 1999 in China. The usual clinical dosage of atorvastatin is 10 mg once daily and may be increased up to 40 mg for patients with hypercholesterolemia. Post-marketing survey of atorvastatin showed that Lipitor® at 10 mg or 20 mg are often be co-administered with brand ezetimibe, EZETROL® 10 mg [Teramoto, T., et al 2012].

In consideration of the efficacy and safety profiles of atorvastatin, and clinical position of MK-0653C, we have found that 10 or 20 mg is an appropriate dose to be combined for atorvastatin.

#### **4.4 Beginning and End of Study Definition**

The overall study begins when the first participant signs the ICF. The overall study ends when the last participant completes the last study-related telephone-call or visit, withdraws from the study, or is lost to follow-up (ie, the participant is unable to be contacted by the investigator).

##### **4.4.1 Clinical Criteria for Early Study Termination**

The clinical study may be terminated early if the extent (incidence and/or severity) of emerging effects/clinical endpoints is such that the risk/benefit ratio to the study population as a whole is unacceptable. In addition, further recruitment in the study or at (a) particular study site(s) may be stopped due to insufficient compliance with the protocol, Good Clinical Practice (GCP), and/or other applicable regulatory requirements, procedure-related problems or an unacceptably high number of discontinuations or withdrawals due to administrative reasons.

### **5 STUDY POPULATION**

Male/Female participants between the ages of 18 and 80 years (inclusive) with hypercholesterolemia and inadequately controlled by low to median dose of statins only (see below) will be enrolled in this study.

Prospective approval of protocol deviations to recruitment and enrollment criteria, also known as protocol waivers or exemptions, is not permitted.

## 5.1 Inclusion Criteria

To be eligible for inclusion in this study, the participant must:

### **Visit 1 and 2 Criteria**

Participants should meet these criteria at Visit 1 and Visit 2.

1. Participant with hypercholesterolemia diagnosed by investigator according to Chinese Guidelines on Prevention and Treatment of Dyslipidemia in Adults (2016 Edition).
2. Participant has been stabilized on atorvastatin treatment at 10 mg (other statins with LDL-C lowering efficacy equivalent to or less than atorvastatin 10 mg) or 20 mg (or other statins with LDL-C lowering efficacy equivalent to 20 mg, refer to [Table 3](#)) for at least 4 weeks prior to Visit 1.

### **Demographics**

3. Participant is male or female.
4. Participant is from 18 years to 80 years of age inclusive, at the time of signing the informed consent.
5. Male Participants

Contraceptive use by men should be consistent with local regulations regarding the methods of contraception for those participating in clinical studies.

A male participant must agree to use contraception as detailed in Appendix 5 of this protocol from the time of providing informed consent through completion of the study and refrain from donating sperm during this period.

### 6. Female Participants

Contraceptive use by women should be consistent with local regulations regarding the methods of contraception for those participating in clinical studies.

A female participant is eligible to participate if she is not pregnant (see Appendix 5), not breastfeeding, and at least one of the following conditions applies:

- Not a woman of childbearing potential (WOCBP) as defined in Appendix 5

OR

- A WOCBP who agrees to follow the contraceptive guidance in Appendix 5 from the time of providing informed consent through completion of the study.

### **Informed Consent**

7. Participant (or legally acceptable representative if applicable) provides written informed consent/assent for the study.

### **Additional Categories**

8. Participant agree to maintained a stable diet and stable exercise during the study.

### **Visit 4 Criteria**

9. Participant has completed the 5-week atorvastatin run-in period.
10. Participant has  $\geq 75\%$  compliance with study medication during the atorvastatin run-in period.
11. Participant meets any of the following criteria on LDL-C level based on the lipid panel test at Visit 3.
  - a. For medium or low risk participants:  $\geq 130$  mg/dL (3.4 mmol/L).
  - b. For high risk participants:  $\geq 100$  mg/dL (2.6 mmol/L) and  $\leq 160$  mg/dL (4.1 mmol/L).
  - c. For very high risk participants:  $\geq 70$  mg/dL (1.8 mmol/L) and  $\leq 160$  mg/dL (4.1 mmol/L).

### **5.2 Exclusion Criteria**

The participant must be excluded from the study if the participant:

### **Visit 1 Criteria**

#### **Medical Conditions**

1. Participant had a uncontrolled hypertriglyceridemia which needs drug intervention or a fasting triglyceride (TG) value  $\geq 500$  mg/dL (4.52 mmol/L) at Visit 1.
2. Participant is currently treated with statin at dose of equivalent LDL-C lowering effect greater than 20 mg atorvastatin.
3. Participants has active liver disease at Visit 1 or lab test evidenced liver transaminases (ALT and AST)  $> 2 \times$  upper limit of normal (ULN) per central laboratory at Visit 1 or local lab within 4 weeks prior to the screening visit.
4. Participant has NYHA (New York Heart Association) Class III or IV symptomatic congestive heart failure at Visit 1.

5. Participant has uncontrolled cardiac arrhythmias, myocardial infarction (MI), PCI, CABG, unstable angina, or stroke within 3 months (12 weeks) prior to Visit 1.
6. Participant has homozygous familial hypercholesterolemia or has undergone LDL apheresis.
7. Participant has endocrine or metabolic disease known to influence serum lipids or lipoproteins (i.e., secondary causes of hyperlipidemia, e.g., hyper or hypothyroidism, Cushing's syndrome) at Visit 1.
8. Participant has an estimated glomerular filtration rate (eGFR)  $< 30 \text{ mL/min}/1.73\text{m}^2$  or other clinical significant renal disease which needs intensive medical care (e.g. systematic use of steroids/immunosuppressant, renal transplant, hemodialysis, etc.) at Visit 1. eGFR calculation is based on the below equation:

Male:  $\text{eGFR } [\text{mL/min}/1.73\text{m}^2] = 194 \times \text{Cr } [\text{mg/dL}]^{-1.094} \times \text{age } [\text{yr}]^{-0.287}$

Female:  $\text{eGFR } [\text{mL/min}/1.73\text{m}^2] = 194 \times \text{Cr } [\text{mg/dL}]^{-1.094} \times \text{age } [\text{yr}]^{-0.287} \times 0.739$

9. Participant has had a gastrointestinal tract bypass, or other significant intestinal malabsorption.
10. Participant has a history of cancer within the past 5 years from Visit 1 (except for successfully treated dermatological basal cell or squamous cell carcinoma or in situ cervical cancer).
11. Participant who is known human immunodeficiency virus (HIV) positive (as assessed by medical history).
12. Participant has hypersensitivity or intolerance to ezetimibe, atorvastatin, the ezetimibe/atorvastatin combination tablet, or any component of these medications or has a condition or situation, which described as contraindication in labeling of EZETROL® or Lipitor® or may interfere with participation in the trial in the opinion of the investigator.
13. Participant has disorders of the hematologic, digestive, or central nervous systems including cerebrovascular disease and degenerative disease that in the opinion of the investigator would limit evaluation or participation.
14. Participant has a history of mental instability, drug/alcohol abuse within the past 5 years, or major psychiatric illness not adequately controlled and stable on pharmacotherapy in the investigator's judgement.
15. Participant has a history of myopathy or rhabdomyolysis with ezetimibe or any statin.
16. Participant has a medical condition or personal circumstance which, in the opinion of the investigator, places the participant at unnecessary risk through continued participation in the trial or does not allow the participant to adhere to the requirements of the protocol.

17. A WOCBP who has a positive urine pregnancy test within 24 hours before the first dose of study intervention. If the urine test is positive or cannot be confirmed as negative, a serum pregnancy test will be required.

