## 10.2 Appendix 2: Clinical Laboratory Tests

- The tests with marker of \* listed in **Table 9** will be performed by the local laboratory at Visit 1.
- Protocol-specific requirements for inclusion or exclusion of participants are detailed in Section 5 of the protocol.
- Additional tests may be performed at any time during the study as determined necessary by the investigator or required by local regulations.

Table 9 Protocol-required Laboratory Assessments

Laboratory Assessments	Parameters					
Hematology*	Platelet Count	RBC Indices: MCV MCH %Reticulocytes		WBC count with Differential: Neutrophils Lymphocytes Monocytes Eosinophils Basophils		
	RBC Count					
	Hemoglobin					
	Hematocrit					
Chemistry*	Blood Urea Nitrogen (BUN)	Potassium	Aspartate Aminotransferase (AST)/ Serum Glutamic-Oxaloacetic Transaminase (SGOT)	Total bilirubin (and direct bilirubin, if total bilirubin is elevated above the upper limit of normal)		
	Albumin	CK (CPK)	Chloride	eGFR		
	Creatinine	Sodium Calcium Potassium Phosphorous Bicarbonate	Alanine Aminotransferase (ALT)/ Serum Glutamic-Pyruvic Transaminase (SGPT)	Total Protein		
	Glucose (fasting)	Uric acid	Alkaline phosphatase (ALP)	$\gamma$ -glutamyl transferase		
Lipid Panel A*	LDL-C	HDL-C non-HDL-C	total cholesterol (TC)	Triglyceride (TG)		
Routine Urinalysis*	Specific gravity	pH, glucose, protein, blood, ketones, [bilirubin, urobilinogen, nitrite, leukocyte esterase] by dipstick		Microscopic examination (if blood or protein is abnormal)		
Apolipoprotein Evaluations	
 
Apolipoprotein B (Apo B)
 
					
Pregnancy test	
 
Urine pregnancy test (urine hCG) will be determined at the site (as needed for WOCBP).
 
Serum <math>\beta</math>-hCG test will be required if urine pregnancy result is positive.
 
					
Other Laboratory Tests	
 
Follicle-stimulating hormone (FSH): only applicable for perimenopausal women.
 
Thyroid stimulating hormone (TSH), fT4
 
					

Laboratory Assessments	Parameters
NOTES:	
* Laboratory tests results received within 4 weeks prior to screening visit is acceptable as screening test to check the eligibility.	

The investigator (or medically qualified designee) must document their review of each laboratory safety report.

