## 2.6 Non-HDL-C

Non-HDL-C refers to the sum of cholesterol in other lipoproteins except for HDL-C. The calculation formula is non-HDL-C = TC - HDL-C. As a secondary target of lipidlowering treatment during the management of atherosclerotic cardiovascular disease (ASCVD) and the high-risk population, non-HDL-C is applicable for individuals with LDL-C levels that are not high or have already reached the treatment goal when the TG level is 2.3-5.6 mmol/L (200-500 mg/dL). International blood lipid guidelines recommend using non-HDL-C as the marker for the primary and secondary prevention of ASCVD.

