### 3.7 Lp (a)

Serum Lp (a) concentration is primarily associated with genetics. Gender, age, body weight, and most cholesterol-lowering drugs do not often affect this concentration. The Lp (a) level in the healthy population shows an obvious skew. Although the level in individuals can reach above 1,000 mg/L, the level in 80% healthy individuals is less than 200 mg/L. Usually, 300 mg/L is used as the cutoff point. People with levels higher than this cutoff are at a significantly increased risk for coronary heart disease, suggesting that Lp (a) causes atherosclerosis. However, clinical evidence is lacking. Furthermore, an increase of Lp (a) can also be observed during various acute phase responses, nephrotic syndrome, diabetic nephropathy, pregnancy, and the administration of growth hormone. After all types of stress increase are excluded, Lp (a) is considered as an independent risk factor for ASCVD.

The expression unit of the values of all blood lipid measurement items is mmol/L according to the national standard of China. Some other countries use mg/dL. The conversion coefficients are: TC, HDL-C, LDL-C: 1 mg/dL = 0.0259 mmol/L; and TG: 1 mg/dL = 0.0113 mmol/L.

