## 8.5 Other dyslipidemia interventions

In addition to active cholesterol interventions, whether other dyslipidemia conditions also require treatment lacks the evidence of relevant clinical trial benefits. The appropriate level of serum TG is < 1.7 mmol/L (150 mg/dL). When serum TG is  $\geq$  1.7 mmol/L (150 mg/dL), non-drug intervention measurement is first applied including therapeutic diet, reduction of body weight, and abstinence from alcohol. If the TG level only shows a mild-to-moderate increase [i.e., 2.3-5.6 mmol/L (200-500 mg/dL)] to manage the risk of ASCVD, then although the reduction of the LDL-C level is the major goal, non-HDL-C should also reach the target value. If non-HDL-C cannot reach the target value even after statin therapy, then fibrates and high purity fish oil preparations should be used additionally with statins. For patients with severe hypertriglyceridemia and fasting TG levels of  $\geq$  5.7 mmol/L (500 mg/dL), drugs that reduce TG and VLDL-C should be considered first (e.g., fibrates, high purity fish oil preparations, or niacin).

For people with HDL-C < 1.0 mmol/L (40 mg/dL), diet should be controlled and lifestyle should be improved. Currently, not enough evidence exists for drug interventions.

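### Exclusion criterion 1 prints 500 mg/dL and 4.52 mmol/L as one triglyceride cut-off, but 4.52 mmol/L is 400 mg/dL and nothing says which figure governs

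*Combined protocol and SAP*

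**What the plan says.** Exclusion criterion 1 (Section 5.2, Visit 1 criteria) has two limbs. The first excludes "uncontrolled hypertriglyceridemia which needs drug intervention", which is left to clinical judgement. The second is numeric and excludes a fasting triglyceride value "\geq 500$ mg/dL (4.52 mmol/L) at Visit 1". Section 5 states that prospective approval of deviations from the enrollment criteria, "also known as protocol waivers or exemptions, is not permitted".

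The guideline in Appendix 7 supplies the conversion in its section 3.7: "TG: 1 mg/dL = 0.0113 mmol/L". The same section adds: "The expression unit of the values of all blood lipid measurement items is mmol/L according to the national standard of China". Elsewhere the guideline pairs 500 mg/dL with two other values: "2.3-5.6 mmol/L (200-500 mg/dL") in section 2.6, and "5.7 mmol/L (500 mg/dL") as the lower bound of severe hypertriglyceridemia in section 8.5.

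Appendix 2 of the protocol says that its asterisked tests, which include Lipid Panel A, "will be performed by the local laboratory at Visit 1". Under Section 8.2.1, central laboratory testing covers Visit 3 to Visit 6. That section also sets the LDL-C method by triglyceride level: Friedewald up to 400 mg/dL, and beta quantification ultracentrifugation above it.

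**The concern.** The parenthesis should restate the mg/dL limit in other units. Instead it gives a lower limit. The synopsis, the schedule of activities, Section 8 and Appendix 2 do not repeat the cut-off, so no second statement settles which figure was meant.

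The mmol/L figure cannot be set aside as secondary. By the guideline's account, lipid results in China are expressed in mmol/L, and Visit 1 lipids are assigned to local laboratories. A site holding an mmol/L report could reasonably compare it with 4.52, and so apply 400 mg/dL while the protocol states 500 mg/dL.

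Three things are at stake: who enters, whether a given enrollment is a deviation, and how the studied population is described. Two sites could treat the same candidate differently, each following the text.

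**Working it through.** **Inputs.** The criterion 1 pair is 500 mg/dL and 4.52 mmol/L (Section 5.2). The triglyceride factor is 0.0113 mmol/L per mg/dL (Appendix 7, guideline section 3.7).

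**Trying to reproduce the printed figure.**

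- mg/dL to mmol/L: 500 × 0.0113 = 5.65 mmol/L, not 4.52.
- mmol/L to mg/dL: 4.52 / 0.0113 = 400.0 mg/dL, not 500.
- Gap: 500 − 400 = 100 mg/dL, and 5.65 − 4.52 = 1.13 mmol/L.
- Ratio: 5.65 / 4.52 = 1.25, so the higher limit is 25% above the lower.

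**Could rounding explain it?** The table converts each printed mmol/L triglyceride value and compares it with its printed mg/dL partner.

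| Place | mmol/L printed | mg/dL printed | mmol/L ÷ 0.0113 | Difference from printed mg/dL |
|---|---|---|---|---|
| Criterion 1 | 4.52 | 500 | 400.0 | −20.0% |
| Guideline 2.6 | 5.6 | 500 | 495.6 | −0.9% |
| Guideline 8.5 | 5.7 | 500 | 504.4 | +0.9% |
| Guideline Table 11 | 2.3 | 200 | 203.5 | +1.8% |
| Guideline Table 11 | 1.7 | 150 | 150.4 | +0.3% |
| Guideline 2.2 | 3.4 | 300 | 300.9 | +0.3% |
| Guideline 10.1.4 | 4.5 | 400 (unit misprinted as mg/day) | 398.2 | −0.4% |

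Every pair except the one in criterion 1 agrees within 2%. The last row shows the guideline itself matching about 4.5 mmol/L with 400. Because 4.52 converts to exactly 400.0, two round thresholds were probably mixed; a misread digit is less likely.

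**Is the fault general?** No. The LDL-C pairs in inclusion criterion 11, checked with the guideline's cholesterol factor of 0.0259, give 70 → 1.81, 100 → 2.59, 130 → 3.37 and 160 → 4.14 mmol/L. The printed values are 1.8, 2.6, 3.4 and 4.1, so all four agree to the printed decimal.

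**Band affected.** Visit 1 fasting triglycerides of 400 to below 500 mg/dL (4.52 to below 5.65 mmol/L), less anyone excluded under the first limb.

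**The case against.** The arithmetic is not in dispute. The case on the other side concerns weight and intent.

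- **Intent looks like 500.** The protocol's lipid criteria put mg/dL first, Section 8.2.1 uses mg/dL alone, and the guideline treats 500 mg/dL as the start of severe hypertriglyceridemia. Providing an LDL-C method above 400 mg/dL also fits a 500 mg/dL limit. These are fair pointers, but none is a rule of precedence. Triglycerides can rise above 400 mg/dL after Visit 1, so the assay provision would be needed under either limit.
- **The first limb may empty much of the band.** Guideline section 8.5 advises adding fibrates and fish oil at 200-500 mg/dL when non-HDL-C stays off target on a statin. Candidates are already on a statin and must miss their LDL-C goal to be randomized, and the non-HDL-C goal is only 30 mg/dL above the LDL-C goal. Many people in the band could therefore be judged to need drugs. This stands as a reason to expect small numbers. It does not resolve the conflict: the decision is the investigator's, and the same advice starts at 200 mg/dL, so it does not define a limit at 400 or 500.
- **Use of 4.52 at sites is inference.** Correct. The documents do not give the units on local reports or in any eligibility check. What is certain is that the text permits either reading.
- **The enrolled population can still be described.** Triglycerides are measured at Visits 1, 3 and 4 and baseline characteristics will be summarized, so the report can show who was randomized. That softens the descriptive harm. It does not tell a site whom to admit.

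**Conclusion.** The concern holds. Criterion 1 states two limits that differ by 100 mg/dL (1.13 mmol/L), and the protocol does not say which applies. This rests only on the printed pair and the conversion factor in Appendix 7.

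The consequence is limited to eligibility, deviation recording and population description for candidates in the band. The ambiguity acts before randomization, so it does not bias the comparison within either cohort or change Type I error or power. LDL-C remains measurable in the band, because Section 8.2.1 provides a method above 400 mg/dL. How many candidates fall there cannot be worked out from the documents. The error should be fixed because it sits in an operative threshold with no waivers; it is not a threat to the trial's conclusions.

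**What to change.** Print one threshold with a matched pair, according to what the sponsor intended: either ≥500 mg/dL (5.65 mmol/L) or ≥400 mg/dL (4.52 mmol/L). Use the same value in the eligibility check.

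When choosing, note that 400 mg/dL is also where the LDL-C method changes. The lower limit would keep people already above that point at Visit 1 out of the trial, although participants could still cross it later under either choice.

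The cost is a one-line protocol correction or a clarification letter, with no added participants, visits or procedures.
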